10.5 Data Analysis

Database lock and primary analyses are planned to occur approximately 2 to 3 months after the last subject is enrolled to complete 6 cycles of study medication. All subjects will continue to be followed up for an additional 6 months after the primary analysis as required by the protocol, i.e., the study will end 12 months after enrollment of the last subject, and a follow-up analysis will be performed at the end of the study.

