The study enrollment period is estimated to be 6 months. 6 months after the last patient enrollment, the database will be locked and the primary analysis will be conducted. After primary analysis, all patients will be followed up for additional 6 months and a follow up analysis will be conducted 12 months after the last patient enrollment.

Eligible patients who have signed informed consent will be enrolled to receive BN101/belumosudil (every 28-day cycle) until cGVHD progression, intolerable toxicity, initiation of a new cGVHD therapy, recurrence of hematological neoplasm, loss to follow-up,

withdrawal of consent, or death, whichever occurs first. During study, concomitant treatment with standard of care systemic cGVHD therapies such as corticosteroids, calcineurin inhibitors (tacrolimus, cyclosporine), sirolimus, MMF, or extracorporeal photopheresis (ECP), are permitted as long as the patient has been on a stable dose / regimen of these per the eligibility criteria. Initiation of new systemic cGVHD therapy while on study is not permitted. Response criteria will be assessed after cycles 1, 2, 3 and 4 and then after every other cycle thereafter (i.e. on Day 1 of Cycle 2, 3, 4, 5, 7, 9, 11 etc). For patients assessed as "Lack of Response - Mixed" and "Lack of Response - Progression" [Evaluated by the investigator based on the National Institutes of Health (NIH) Consensus Development Project on Criteria for Clinical Trials in cGVHD(2014), hereinafter referred to as the NIH Consensus Criteria (2014)], if the investigator believed that these patients could continue to benefit from treatment with BN101/belumosudil, the treatment may be continued after a written application was submitted, and approval from the Sponsor's Medical Monitor as well as documentation of the patient's willingness to continue treatment was obtained. For patients who did not achieve any response after 12 cycles of BN101/belumosudil treatment, they should discontinue the study medication and withdraw from the study if in the investigator's judgment there is no evidence of clinical benefit (e.g., improvements in organ score, improvements in Lee symptom scores, reductions of corticosteroid/tacrolimus doses). For patients whose cGVHD has not progressed at the time of discontinuation of the study treatment and who come off study for reasons other than AEs should be tapered off BN101/belumosudil by reducing the dose every other week (200mg QD → 200mg QOD → discontinue).

5. Study Endpoints

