5.1.2. Secondary Efficacy Endpoints

Secondary efficacy endpoints include Duration of Response (DoR), Lee Symptom Scale Score (LSS), Response by Organ System, Time to Response, Time to Next Therapy, Corticosteroid Dose, Calcineurin Inhibitor (CNI) Dose, Failure Free Survival (FFS), Overall Survival (OS), Change in cGVHD severity using the Clinician-Reported Global cGVHD Activity Assessment, and Change in symptom activity using the cGVHD Activity Assessment Patient Self-Report.

DoR

Four definitions of DoR are as following:

The primary definition of DoR is the time from first documentation of response to the time of first documentation of deterioration from best response (e.g., CR to PR, or PR to LR).

The secondary definition of DoR is the time from first documentation of response to the time of first documentation of lack of response.

The tertiary definition of DoR is the time from first documentation of response to the time of initiation of new systemic cGVHD therapy.

The quaternary definition of DoR is the time from first documentation of response to the time of first documentation of lack of response (as the secondary definition) but with durations summed for multiple response / lack of response episodes.

The DoR will be reported only for responders. And the censoring rules in [Table 2](#) will be applied.

Lee Symptom Scale Score (LSS)

Lee cGVHD Symptom Scale will be assessed on Day 1 of Cycles 2-5, then on Day 1 of every other Cycle thereafter and EOT. The questionnaire consists 30 items of 7 domains: skin, eyes and mouth, breathing, eating and digestion, muscles and joints, energy, and emotional. Each question is scored 0, 1, 2, 3 or 4.

A domain score will be calculated for each domain by taking the mean of all items completed if more than 50% were answered and normalizing to a 0 to 100 scale. A summary score will be calculated as average of all domain scores if more than 50% of them are nonmissing. A higher score indicated more bothersome symptoms. 7 points difference on the summary score of cGVHD symptom scale was found to be clinically meaningful.

$Raw\ Score = (I_1 + \dots + I_m) / m$, m is the number of items have nonmissing value in a domain.

$$Domain\ Score = Raw\ Score / 4 * 100.$$

$Summary\ Score = (Domain\ Score_1 + \dots + Domain\ Score_n) / n$, n is the number of domains have nonmissing domain scores.

Response by Organ System

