8.4.2. Analyses for Secondary Endpoints

DoR

DoR will be analysed only based on responder population. Kaplan-Meier plots and descriptive statistics of DoR will be provided. The censoring rules in [Table 2](#) will be applied. Landmark analyses with number and percentage of patients with response sustained for ≥ 12 , ≥ 16 , ≥ 20 , ≥ 24 , ≥ 32 , ≥ 40 and ≥ 48 weeks will be provided.

Table 2 Censoring Rules for Duration of Response

| DoR | Events | Censoring |
|------------|--|--|
| Primary | 
 • Deterioration from best response • Initiation of new systemic therapy for cGVHD • Death 
If deterioration from best response or initiation of new systemic therapy happens immediately after two or more missed response assessments, the event date should be set as four weeks (one cycle) after last documented response assessment prior this event.
 | Last documented response assessment |
| Secondary | 
 • Documented LR • Initiation of new systemic therapy for cGVHD • Death 
If LR or initiation of new systemic therapy happens immediately after two or more missed response assessments, the event date should be set as four weeks (one cycle) after last documented response assessment prior this event.
 | |
| Tertiary | 
 • Initiation of new systemic therapy for cGVHD • Death | Last response assessment or long term follow up assessment, whichever is the latest and available. |
| Quaternary | 
 • LR • Initiation of new systemic therapy for cGVHD • Death 
With summation of DoR from multiple episodes.
 | Same with censoring rule for primary and secondary. |

Lee Symptom Scale Score (LSS)

The analyses will be performed based on mITT, responder and nonresponder population. The analyses will include:

- Both scores and change from baseline values (summary score and domain scores) will be summarized as continuous variables by visit.
- Number and percent of patients with a ≥ 7 point reduction (7-PtR) from baseline.

- Number and percent of patients with a 7-PtR from baseline on 2 consecutive assessments.
- Duration of a 7-PtR (DO7-PtR) (defined as time from documentation of the first \geq 7-point resolution to the first documentation of less than 7-point reduction). If there are multiple episodes, the DO7-PtR will be measured as the sum of DO7-PtR from all episodes.

Response by Organ System

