The best response (CR, PR) for the nine individual organs plus global severity rating will be summarized. Time to response at the organ level will also be evaluated. Descriptive statistics and plots of cumulative number and percentage of responders over time will be provided. Two series of percentages will be presented:

- With total number of patients in mITT with involvement of the given organ at baseline as denominator
- With numbers of patients in the responder population with involvement of the given organ at baseline as denominator

Time to Response (TTR)

Descriptive statistics and plots of cumulative number and percent of responders over time will be provided. TTR analyses will only be conducted for the responder population.

Time to Next Therapy (TTNT)

TTNT will be analysed by the Kaplan-Meier survival method as well as the landmark analysis at 3, 6, 9, and 12 months.

Corticosteroid Dose

Corticosteroid doses will be presented as prednisone equivalent dose. Descriptive statistics for the mITT population, responder / nonresponder populations will be provided for:

- Systemic corticosteroid dose over time
- Change and percent change from baseline (C1D1) to the greatest corticosteroid dose reduction during BN101/belumosudil treatment period
- Number and percentage of patients who reduced systemic corticosteroid dose during BN101/belumosudil treatment period
- Number and percentage of patients who ever discontinued systemic corticosteroid usage for over 28 days during BN101/belumosudil treatment period

The above analyses will be censored on or after new systemic cGVHD treatment.

Calcineurin Inhibitor (CNI) Dose

CNI includes systemic tacrolimus and cyclosporine. Descriptive statistics will be provided for:

- Number and percentage of patients who reduced CNI dose during BN101/belumosudil treatment period
- Number and percentage of patients who ever discontinued CNI during BN101/belumosudil treatment period

Failure Free Survival (FFS)

Kaplan-Meier plots, descriptive statistics of FFS and landmark FFS at 3, 6, 9, and 12 months will be provided. In addition, analyses for the three components of FFS will also be provided.

Overall Survival (OS)

Kaplan-Meier plots, descriptive statistics of OS and landmark OS at 3, 6, 9, and 12 months will be provided.

Change in cGVHD severity using the Clinician-Reported Global cGVHD Activity Assessment

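### SAP 8.4.2 gives DoR landmarks as number and percentage with no censoring-adjusted estimator; read as simple percentages, they understate durability at the primary analysis, mainly from 24 weeks

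*SAP*

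**What the plan says.** SAP 8.4.2 analyses DoR in responders only. It plans Kaplan-Meier plots and descriptive statistics under the Table 2 censoring rules, and then adds: "Landmark analyses with number and percentage of patients with response sustained for" seven thresholds from 12 to 48 weeks.

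Table 2 lists events and censoring dates for each of four DoR definitions. For the primary and secondary definitions, a responder without an event is censored at the "last documented response assessment". Tertiary DoR may instead be censored at a long-term follow-up contact. The quaternary definition follows the secondary one, "but with durations summed for multiple response / lack of response episodes" (SAP 5.1.2).

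The landmarks for other endpoints are worded differently. For example, "TTNT will be analysed by the Kaplan-Meier survival method as well as the landmark analysis at 3, 6, 9, and 12 months"; no number and percentage is mentioned there, nor for FFS or OS. Protocol 10.6.2.2 plans Kaplan-Meier medians and quartiles for DoR and says nothing about landmarks.

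On accrual, SAP section 4 states: "The study enrollment period is estimated to be 6 months". For the first data cut it then gives this rule: "6 months after the last patient enrollment, the database will be locked and the primary analysis will be conducted". Its assessment schedule reads: "Response criteria will be assessed after cycles 1, 2, 3 and 4 and then after every other cycle thereafter". A follow-up analysis comes 12 months after last enrollment. Protocol 10.5 places the first lock differently: "Database lock and primary analyses are planned to occur approximately 2 to 3 months after the last subject is enrolled to complete 6 cycles".

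**The concern.** A number and percentage of responders is a count over a fixed denominator. A responder who is still responding, but whose last assessment precedes the landmark, stays in the denominator and cannot enter the numerator. The result mixes loss of response with short follow-up. At a lock 6 months after last enrollment many responders will be in that position for the later landmarks.

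The trial is a bridging study meant to show consistency with KD025-213, and durability is part of that picture. The same section could produce a landmark table and a Kaplan-Meier curve that disagree widely at the same week, with the table making responses look shorter than they are.

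**Working it through.** The documents give no DoR landmark figure, so there is none to reproduce.

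**Inputs**
- Assessments at Day 1 of Cycles 2, 3, 4, 5, 7, 9 and so on, in 28-day cycles: weeks 4, 8, 12, 16, 24, 32, 40, 48, 56.
- Enrollment about 26 weeks and lock 26 weeks after the last patient (SAP 4): follow-up from 26 to 52 weeks. Uniform accrual is assumed.
- Median DoR 35 weeks (KD025-208) and 21.1 weeks (KD025-213, 200 mg QD), both from protocol 1.4.2. These are used as assumptions with an exponential shape; the documents do not say which DoR definition produced them.

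**Step 1: longest observable DoR, first response at week 4.** Last patient enrolled: last visit week 24, so 24 − 4 = 20 weeks. First patient enrolled: last visit week 48, so 48 − 4 = 44 weeks.

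**Step 2: ceiling if no responder ever loses response.** A patient first responding at week t can show DoR ≥ L only if follow-up reaches v, the first visit at or after t + L. Ceiling = (52 − v)/26, limited to 0–100%. For t = 4 and L = 24/32/40/48, v = 32/40/48/56, giving 20/26, 12/26, 4/26 and 0.

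| First response | 12 wk | 16 | 20 | 24 | 32 | 40 | 48 |
|---|---|---|---|---|---|---|---|
| Week 4 | 100% | 100% | 100% | 77% | 46% | 15% | 0% |
| Week 8 | 100% | 100% | 77% | 77% | 46% | 15% | 0% |
| Week 12 | 100% | 77% | 77% | 46% | 15% | 0% | 0% |
| Week 16 | 77% | 77% | 46% | 46% | 15% | 0% | 0% |

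The true value in every cell is 100%. An illustrative mix of 50/25/15/10% first responding at weeks 4/8/12/16 (assumed) gives 98/94/85/69/38/12/0%.

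**Step 3: with loss of response, week-4 responders.** Loss is dated at the next visit. Visit-dated DoR reaches 24/32/40 weeks if the patient is still in response at DoR 20/28/36 weeks and the following visit precedes the cut. For median m, Kaplan-Meier estimates 2^(−20/m), 2^(−28/m) and 2^(−36/m); the simple percentage multiplies each by the Step 2 ceiling.
- m = 35: Kaplan-Meier 67/57/49%; simple 0.769 × 0.673 = 52%, 0.462 × 0.574 = 26%, 0.154 × 0.490 = 8%.
- m = 21.1: Kaplan-Meier 52/40/31%; simple 40/18/5%.

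Dating losses at visits makes Kaplan-Meier itself slightly high (2^(−24/35), 2^(−32/35), 2^(−40/35) = 62/53/45%), but it is far closer than the simple figure. Dropping responders censored before the landmark does not repair the percentage. At m = 21.1 and 24 weeks it gives 0.399/(0.399 + 0.482) = 45%, still below 52%.

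**Step 4: dependence on accrual and lock.** Week-4 ceilings at 24/32/40/48 weeks:
- 52-week accrual (assumed), follow-up 26–78 weeks: 46/52, 38/52, 30/52, 22/52 = 88/73/58/42%.
- Protocol 10.5 lock with 26-week accrual. Six cycles plus 2 months is 24 + 8.7 = 32.7 weeks after last enrollment: 100/72/41/10%. Six cycles plus 3 months is 24 + 13 = 37 weeks: 100/88/58/27%.

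**Step 5: 12-month analysis, follow-up 52–78 weeks.** Patients still on drug have an end-of-treatment visit at the end of the main study, and protocol 4.3.4 and Appendix 1 include a cGVHD response assessment in it. The requirement becomes follow-up of at least t + L. At 40 weeks the ceiling is 100% for first response at weeks 4, 8 and 12, and (78 − 56)/26 = 85% at week 16. At 48 weeks it is 100%, 22/26 = 85%, 18/26 = 69% and 14/26 = 54% for weeks 4/8/12/16. Landmarks below 40 weeks reach 100%.

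**The case against.** The strongest reply is that the sentence just before the landmark sentence applies Table 2 to DoR, in a paragraph that opens with Kaplan-Meier plots, so the landmarks may be meant to be read off that curve. A reader might infer from the gap that the SAP has no censoring rule for DoR. It does: Table 2 gives the dates. What is missing is the link from those dates to the landmark figures, and the wording used (number and percentage) points to a count. If Kaplan-Meier was intended, one sentence settles it.

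Second, a reader might infer that the 48-week figure must be 0%. That follows only from the estimated 6-month accrual and the SAP lock. The synopsis study duration of about 2 years, with study end 12 months after last enrollment, is compatible with longer accrual, and Step 4 shows non-zero ceilings. This objection stands.

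Third, a reader might infer that the distortion persists at the final analysis. The assessment at the end-of-main-study visit removes most of it; a shortfall remains chiefly at 48 weeks for later responders.

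Fourth, a count described as observed is not wrong in itself, every analysis is descriptive, and the sizes rest on assumed response times and an exponential DoR; Table 2 events such as death or new therapy need not fall on visit dates. All of this stands and limits the weight of the point. It does not remove the gap, because the ceilings in Step 2 need no assumption about how long responses last.

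**Conclusion.** The concern holds as a minor point about one supplementary output. Read as simple percentages, the primary and secondary DoR landmarks at the primary analysis are biased downward as measures of sustained response. For week-4 responders the bias starts at 24 weeks; later responders also lower the 12- to 20-week figures modestly. With a 35-week median the shortfall against Kaplan-Meier is about 15, 31 and 41 percentage points at 24, 32 and 40 weeks (67 − 52, 57 − 26, 49 − 8).

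These sizes assume uniform 26-week accrual, the SAP lock date, the nominal visit grid and exponential DoR. The visit-grid figures do not describe tertiary or quaternary DoR. The documents do not support any inference that ORR, the Kaplan-Meier plots or the DoR medians are affected.

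**What to change.** In SAP 8.4.2:
- For the primary, secondary and tertiary DoR definitions, report each landmark as the Kaplan-Meier probability of continued response with 95% CI and number at risk, under the Table 2 censoring rules.
- At the primary analysis, mark landmarks beyond the longest observed DoR as not estimable and report them at the 12-month analysis.
- Label any simple counts, including those for the summed-episode quaternary DoR, as observed, and show the number censored before each landmark.

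The cost is a few sentences and some extra output from a Kaplan-Meier run already planned; no new data are needed. The downside is imprecision. With about 22 responders (30 × 73%, the KD025-213 rate), all first responding at week 4, and a 35-week median, the expected number at risk at 24/32/40 weeks is 22 × 0.518, 22 × 0.265 and 22 × 0.075, or about 11, 6 and 2. The chance that nobody is at risk at 40 weeks is about 0.925^22 = 18%. Showing the number at risk makes that visible.

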6.4.2 Systemic cGVHD Therapies

Per the eligibility criteria, subjects receiving standard of care systemic cGVHD therapies such as calcineurin inhibitors (tacrolimus, cyclosporine), sirolimus, MMF, methotrexate, rituximab or ECP, may be enrolled if they have been on a stable dose/schedule. During the study treatment period, it is permissible to continue cGVHD treatment as described above at doses/regimens that have stabilized prior to enrollment, but it is not permissible to increase the dosage of these medications unless the increase in dosage is used only to maintain the current therapeutic level of the medication (e.g., to maintain the current blood concentration). Doses and schedules of these therapies will be collected throughout the study and changes will be documented.

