10.6.2.2 Secondary Efficacy Endpoints

Secondary endpoints are as follows:

- DoR, defined as the time from the first evaluation of CR or PR to the confirmed occurrence of cGVHD progression. For subjects who had not experienced cGVHD progression at the end of the study, the date of their last objective evaluation was used as the DoR censoring date.
- Changes in the Lee Symptom Scale Score: Analyses will include:
 - Number of subjects with a \geq 7 point reduction
 - Number of subjects with a \geq 7 point reduction on 2 consecutive assessments
 - Duration of a \geq 7 point reduction
- Response by organ system: The response assessment for the nine individual organs (Skin, Eyes, Mouth, Esophagus, Upper GI, Lower GI, Liver, Lungs, and Joints and fascia).
- Number and percentage of subjects who have a best response of PR and number and percentage of subjects who have a best response of CR.
- Change in corticosteroid dose
- The prednisone equivalent dose of corticosteroids (mg/kg/day) during the study will be analyzed.
- Change in calcineurin inhibitor dose.
- FFS, FFS is defined as the absence of cGVHD treatment change, non-relapse mortality and recurrent malignancy. Median FFS (from first dose of BN101/Belumosudil) and landmark FFS at 1 year(if applicable) will be analyzed.
- OS, defined as time from first dose of BN101/belumosudil to the date of death due to any
 cause.
- Changes in cGVHD global severity rating using the Clinician-Reported Global cGVHD Activity Assessment
- Changes in symptom activity using the cGVHD Activity Assessment Patient Self-Report

Descriptive statistics will be provided for all secondary endpoints.

For DoR (only for subjects determined to have CR and/or PR), FFS, and OS, the median, first quartile, third quartile, and their two-sided 95% CIs were calculated using the Kaplan-Meier method, and survival curves were plotted.

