Response assessment by physician for the nine individual organs (skin, eyes, mouth, esophagus, upper GI, lower GI, liver, lungs and joints and fascia) plus global severity rating will be collected in eCRF.

Time to Response (TTR)

TTR is defined as the time from first treatment to the time of first documentation of response.

Time to Next Therapy (TTNT)

TTNT is defined as the time from first treatment to the time of new systemic cGVHD treatment, censored by last response assessment or long term follow up assessment, which ever is the latest and available.

Corticosteroid Dose

Corticosteroid doses will be presented as mg/kg/day prednisone equivalent dose. If a patient is not using prednisone as the systemic corticosteroid, then the prednisone dose equivalent will be determined according to following conversion ratios:

1mg prednisone is equivalent to:

- 4mg Hydrocortisone
- 0.8mg Methylprednisolone
- 0.15mg Dexamethasone

- 1mg Prednisolone
- 0.8mg Triamcinolone

Transient increase in corticosteroid dosing (not exceeding 1mg/kg/day prednisone equivalent) is permitted for the treatment of cGVHD flare, but dose must be reduced back to the pre-enrollment dose within 6 weeks. If the dose remains elevated for more than 6 weeks, this will be considered a BN101/belumosudil treatment failure. More than 2 episodes of cGVHD flare requiring increased corticosteroid in the first month of BN101/belumosudil treatment will also be considered a BN101/belumosudil treatment failure.

Calcineurin Inhibitor (CNI) Dose

CNI includes systemic tacrolimus and cyclosporine.

Failure Free Survival (FFS)

FFS is defined as the absence of new cGVHD systemic therapy, non-relapse mortality and recurrent malignancy (e.g. underlying disease) and is censored by last response assessment or long term follow up assessment, whichever is the latest and available.

Overall Survival (OS)

OS is defined as time from first dose of BN101/belumosudil to the date of death due to any cause.

Change in cGVHD severity using the Clinician-Reported Global cGVHD Activity Assessment

The Clinician-reported global cGVHD Activity Assessment is a 0-10 point numeric rating scale with a score 0 indicating “cGVHD symptoms not at all severe” and a score of 10 being “most severe cGVHD symptoms possible”. The activities are assessed on Day 1 of each cycle from Cycle 1 Day 1 to EOT.

Change in symptom activity using the cGVHD Activity Assessment Patient Self-Report

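### The SAP narrows the loosely worded endpoint of change in calcineurin inhibitor (CNI) dose to two downward-only counts, with no planned summary of size of change, unchanged doses or increases

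*SAP*

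**What the plan says.** Protocol 10.6.2.2 names the endpoint only as "Change in calcineurin inhibitor dose", with no unit, baseline, time point or summary statistic, and adds that "Descriptive statistics will be provided for all secondary endpoints". On data, Protocol 6.4.2 states for the permitted background cGVHD therapies, CNIs included: "Doses and schedules of these therapies will be collected throughout the study and changes will be documented". The same section bars raising their doses "unless the increase in dosage is used only to maintain the current therapeutic level of the medication".

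SAP 5.1.2 defines the endpoint just by naming the drugs: "CNI includes systemic tacrolimus and cyclosporine". SAP 8.4.2 then plans two outputs: "Number and percentage of patients who reduced CNI dose during BN101/belumosudil treatment period" and "Number and percentage of patients who ever discontinued CNI during BN101/belumosudil treatment period".

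For corticosteroids, immediately above in SAP 8.4.2, there are four outputs. One is dose over time, and another is "Change and percent change from baseline (C1D1) to the greatest corticosteroid dose reduction during BN101/belumosudil treatment period".

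**The concern.** Both planned CNI outputs look in one direction. A patient whose dose rose and a patient whose dose never moved fall into the same unreported remainder. No minimum size or duration is set for a reduction, so a short small cut has the same weight as a sustained large one, and a patient who was cut and later raised again still counts as reduced.

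The trial has one arm, so no control group shows how often CNI doses drift down anyway. A table that can only record reductions and stops invites the reading that the drug spares CNI use, and nothing else planned would let a reader test that. The reading matters somewhat, because Protocol 3.3 gives a lower tacrolimus dose as one example of clinical benefit.

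**Working it through.** The plan states no figure for this endpoint, so the check is a comparison of texts followed by one illustration.

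**Planned outputs for the two dose endpoints (SAP 8.4.2)**

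| | Corticosteroid | CNI |
|---|---|---|
| Outputs planned | 4 | 2 |
| Giving dose level or size of change | 2 | 0 |
| Count reduced | yes | yes |
| Count discontinued | yes, for over 28 days | yes, no minimum time |
| Count increased or unchanged | no | no |

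The steroid percent change is taken to the greatest reduction, so it too looks downward. The steroid summary of dose over time, however, would show a rise, and CNI has no equivalent. Elsewhere the SAP does report both directions: for PROMIS (8.4.3) it counts patients with a 4.7-point reduction and patients with a 4.7-point increase.

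**Are the data available?** Yes. Protocol 6.4.2 has doses and changes recorded throughout, and the schedule of assessments collects cGVHD therapies until 28 days after the last dose.

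**Can increases occur?** Yes, within the exception in Protocol 6.4.2. An increase outside that exception would be equally absent from the CNI outputs.

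**Related gaps in the same text.** The denominator (baseline CNI users or all mITT patients) is not given. Censoring at new systemic cGVHD treatment is written under corticosteroids and not under CNI.

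**Illustration of the one-directional count.** The assumptions here are mine, not the documents'. Take six visits (the first six response visits are Cycles 2, 3, 4, 5, 7 and 9). At each visit the dose moves with probability 0.2, equally likely one step up or down, with no discontinuation. Expected change is zero. Let S be the net number of steps after six visits.

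- P(S = 0) = 0.8^6 + 30(0.1^2)(0.8^4) + 90(0.1^4)(0.8^2) + 20(0.1^6) = 0.2621 + 0.1229 + 0.0058 + 0.0000 = 0.391
- P(S < 0) = (1 − 0.391)/2 = 0.305, and P(S > 0) is the same
- P(S = −1) = 6(0.1)(0.8^5) + 60(0.1^3)(0.8^3) + 60(0.1^5)(0.8) = 0.1966 + 0.0307 + 0.0005 = 0.228
- P(S ≤ −2) = 0.305 − 0.228 = 0.077
- By reflection, P(below baseline at some visit) = P(S < 0) + P(S ≤ −2) = 0.305 + 0.077 = 0.381

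About 38% would be below baseline at some visit, and by symmetry about 38% above it at some visit. The 0.077 is also the share who dipped below baseline but were back at or above it by the last visit. With move probabilities of 0.1 and 0.3 the 38% becomes 24% and 47%. The planned table would show only the downward figure. The model shows the mechanism and does not predict this cohort.

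**The case against.** The strongest reply is that the protocol never says what statistic change in CNI dose means. It gives corticosteroids a scale (prednisone equivalent, mg/kg/day) and allows tapering after at least two weeks. It gives CNIs neither, and the documents contain no common dose scale for tacrolimus and cyclosporine. Counts of patients who reduced or stopped are descriptive statistics of dose change. This stands, and it rules out one reading that a reader might infer: that the protocol endpoint is dropped or not produced. The SAP narrows an undefined endpoint and contradicts no formula.

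Three other inferences also go too far.

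- *That increases will never be reported.* SAP 8.2.1 implies a listing of concomitant medication that might show CNI records. What can be said is that no summary of increases is planned.
- *That permitted increases mean intensified treatment offsetting the reductions, or that a dose table would show whether exposure fell.* Protocol 6.4.2 limits increases to holding the current level, which separates dose from exposure.
- *That the loss can be stated as statistical power.* SAP section 6 rules out formal tests. A log-dose model is undefined for patients who stop, many doses may not change at all after a stable entry regimen, and the documents give no CNI reduction rate to assume.

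What the reply does not answer is the asymmetry. The lack of a common scale is met by using percent of each patient's own baseline, and an undefined endpoint is a reason for the SAP to define it in both directions.

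**Conclusion.** The point holds as a cheap improvement. SAP 8.4.2 gives two CNI outputs, both downward, and none that shows size of change, unchanged dose or increase. Followed exactly, the summary could read as CNI-sparing in a cohort whose net dose did not fall.

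The conclusion rests on the SAP text as it stands, on CNI doses being recorded as Protocol 6.4.2 says, and on no CNI summary being planned elsewhere in the SAP; none was found. How far the counts would mislead in practice cannot be computed from the documents, which give neither the number of CNI users nor how often their doses change. The 24% to 47% in the illustration depends wholly on its assumptions. The impact is limited to one descriptive secondary endpoint, and the primary ORR analysis is unaffected.

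**What to change.** In SAP 8.4.2, under CNI dose, for patients on a CNI at baseline:

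- Add percent change from baseline dose (median and quartiles) by visit and at the last on-treatment assessment, for tacrolimus and cyclosporine separately and pooled as percent of baseline, with discontinuation counted as −100%.
- Add the number and percentage increased, unchanged, reduced and discontinued at the last on-treatment assessment.
- Keep the two existing counts.
- State whether the censoring at new systemic cGVHD treatment, now written for corticosteroids, applies to CNI as well.
- Footnote that doses are titrated to blood level, so dose change is noisy and does not measure exposure.

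The cost is SAP wording and one extra descriptive table from data already collected. No clinical rule changes. The downside is the titration noise, which the footnote covers.
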